6.3.4 Duration of Best Response

The duration of overall response is measured from the time measurement criteria are met for best response until the first date that recurrent or progressive disease is objectively documented.

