1.1.2 Secondary Objectives

- To determine best response rates according to International Myeloma Working Group criteria after 8 cycles of CRd combination therapy
- To determine progression free survival (PFS)
- To determine duration of response (DOR)
- To determine overall survival (OS)
- To evaluate biological activity of carfilzomib and correlate to clinical outcomes, including gene expression profiling on pre- and post-carfilzomib exposure bone marrow samples
- To assess the impact of minimal residual disease by flow cytometry and PET/CT in relation to outcome

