6.3 RESPONSE CRITERIA

6.3.1 Timing

Response assessments will be performed Day 1 of every cycle during Cycles 1-8 and every third cycle during Cycles 9-20: Cycles 9, 12, 15 and 18 and every third cycle during Cycles 21-32: Cycles 21, 24, 27, 30 and end of 32.

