- Development of hypercalcemia that can be attributed solely to the plasma cell proliferative disorder

- **Relapse from CR**

Any one or more of the following:

- Reappearance of serum or urine M-protein by immunofixation or electrophoresis. (Appearance of monoclonal or oligoclonal bands that are different from original isotype may not be defined as “relapse from CR”. Oftentimes, such bands may indicate fluctuations in immunological parameters that are not reflective of MM disease. In these situations, immunofixation and electrophoresis will be interpreted by the clinician before being labeled as “relapse”. ([32](#), [33](#)))
- Development of $\geq 5\%$ plasma cells in the bone marrow
- Appearance of any other sign of progression (i.e., new plasmacytoma, lytic bone lesion, hypercalcemia)

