6.3.5 Progression-Free Survival

PFS is defined as time of start of treatment to time of progression or death, whichever occurs first.

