6.3.7 Overall response rates after 8 cycles

Overall response rates (ORR) is PR+VGPR+CR after 8 cycles of therapy.

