10.3.2 Analysis of the Secondary Endpoints

Secondary endpoints are to estimate overall response rates (ORR) according to International Myeloma Working Group criteria after 8 cycles(31), progression free survival (PFS), duration of response and overall survival. Progression free survival, duration of response and overall survival will be estimated using the Kaplan-Meier method and reported along with 95% confidence intervals at appropriate time points.

A number of correlative studies will be performed in order to assess carfilzomib in vitro biological activity and investigate minimal residual disease in MM. Minimal residual disease will be further explored using multi-parametric flow cytometry and PET-CT imaging.

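### Duration of response is timed from best response although overall response means PR or better, which shortens it only in patients whose response deepens; its end events also do not match PFS

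*Combined protocol and SAP*

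**What the plan says.** The combined protocol and SAP lists duration of response (DOR) as a secondary objective in 1.1.2. Section 10.3.2 gives the analysis: "Progression free survival, duration of response and overall survival will be estimated using the Kaplan-Meier method", with 95% confidence intervals. Section 10 gives no start date, event list or censoring rule for it.

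The only definition is in 6.3.4. The heading is *Duration of Best Response*. The sentence beneath it reads "The duration of overall response is measured from the time measurement criteria are met for best response" and continues "until the first date that recurrent or progressive disease is objectively documented". Section 6.3.7 shows what overall response covers: "Overall response rates (ORR) is PR+VGPR+CR after 8 cycles of therapy".

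For PFS, 6.3.5 states: "PFS is defined as time of start of treatment to time of progression or death, whichever occurs first". Section 6.3.3.1 lists Relapse from CR as a category apart from progressive disease. One of its triggers is "Reappearance of serum or urine M-protein by immunofixation or electrophoresis".

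**The concern.** The endpoint's name, the section heading and the defining sentence do not agree. A duration of overall response, with overall response meaning PR or better, would start when PR or better is first reached. The sentence starts the clock at the best category instead. A patient who moves from PR to VGPR to CR has the time spent in the earlier categories removed, while a patient who reaches PR and stays there keeps all of it. The reported DOR would then understate time in response in the patients who do best on treatment.

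A second, separate problem is the end of the interval. DOR and PFS are to be reported side by side from the same patients, but they name different events, and nothing says how a death without progression enters the DOR curve. Two analysts could produce different DOR curves from the same data and both claim to have followed the plan.

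**Working it through.** **Figures in the plan.** The documents give no figure for DOR. The only design figures concern the primary endpoint: the probability of 5 or more events in 45 is stated as 7.3% at a true rate of 5% and 82.5% at 15%. Exact binomial tails give 7.29% and 82.52%, so these reproduce. They do not depend on the DOR definition.

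**Effect of the start date.** Let F be the date of first PR or better, B the date best-response criteria are met, and E the end of the interval (event or censoring). With the same end date:

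DOR from best = E − B = (E − F) − (B − F) = DOR from first − lag.

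The lag is zero when the first response is also the best, and positive only when response deepens.

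**Largest lag on the plan's schedule.** Inputs:
- Cycles last 28 days (Précis).
- Section 6.3.1 sets the assessments: "Response assessments will be performed Day 1 of every cycle during Cycles 1-8 and every third cycle during Cycles 9-20", then every third cycle to the end of Cycle 32.
- The first assessment after the start of treatment is therefore Cycle 2 Day 1, at 28 days. Placing first response there is an assumption that gives the maximum.

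The end of Cycle k falls at 28k days, so the lag is 28k − 28. Months use 30.4375 days.

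| Best response reached by | Days from start | Lag | Months |
|---|---|---|---|
| End of Cycle 8 | 224 | 224 − 28 = 196 | 6.4 |
| End of Cycle 20 | 560 | 560 − 28 = 532 | 17.5 |
| End of Cycle 32 | 896 | 896 − 28 = 868 | 28.5 |

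Delays are excluded. The stem cell harvest delay of up to 5 weeks (3.1, 3.2.4) would add up to 35 days to a lag that spans it.

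**Which rows apply.** Section 1.1.2 ties best response rates to 8 cycles, which points to the first row. The Study Calendar notes (3.4) provide for CR being achieved in Cycles 9-20 and 21-32. The plan does not say whether such a CR resets best response for 6.3.4, so the lower two rows are conditional.

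**Illustration on the Kaplan-Meier median.** The assumptions here do not come from the documents: exponential duration from first response, and half of responders assigned a deepening lag, uniform on 2 to 17.5 months, counted only if they are still event-free. This uses the later-deepening reading. With 100,000 simulated patients, a true median of 24, 36 or 60 months from first response becomes about 19.6, 31.4 or 55.2 months from best response. In the 36-month case the median among deepeners falls from 45.6 to 35.8. Among the others it stays at 28.0.

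**End events side by side.**
- DOR (6.3.4): recurrent or progressive disease. Death is not named.
- PFS (6.3.5): progression or death. Recurrence is not named.
- Relapse from CR (6.3.3.1): reappearance on immunofixation is enough. Progression on serum M-component needs a rise of at least 25% and at least 0.5 g/dl on two consecutive measurements.

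This difference has no single direction. Counting relapse from CR could end DOR before a PFS event. Censoring deaths lengthens DOR: in the 36-month simulation, if 10% or 20% of events are deaths and are censored, the median from best response is 35.2 or 40.5 months, against 31.2 or 31.5 with deaths counted as events.

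**The case against.** The strongest reply is the heading. A section called Duration of Best Response that starts at best response is consistent with itself, and the slip may be only the word overall. That reading is possible, but it does not remove the problem: the sentence is then mislabelled, and the DOR of 1.1.2 and 10.3.2 has no definition at all.

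It can also be said that the endpoint is descriptive, in a single-arm trial with no DOR hypothesis, and that PFS, timed from start of treatment, carries no such loss. Both points are right, and they limit the importance of the defect.

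Several stronger readings are tempting, but the documents do not support them:
- A reader might infer that the end-event mismatch also shortens DOR. It does not act in one direction, and the shortening comes from the start date alone.
- A reader might infer that immunofixation relapse from CR ends DOR while PFS continues. The term recurrent is undefined, 6.3.3.1 uses relapse within the progression criteria and progression within the relapse criteria, and 6.3.5 does not exclude relapse from CR. The divergence is possible, not established.
- A reader might take the median of 7 cycles in 1.2.10 as time to best response. The text does not say that; it may be the number of cycles received.
- A reader might add that the result cannot be compared with other trials. The documents set no DOR benchmark and plan no such comparison.
- A reader might object that the date of best response is known only in hindsight. A first response confirmed on two consecutive determinations (6.3.2) is also fixed only afterwards, so this argument carries little weight.

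**Conclusion.** The point stands. The only definition available for DOR starts an overall-response duration at best response, and the text needs correcting on either reading of 6.3.4. As written, DOR loses the first-to-best lag, and only in patients who deepen. The loss is at most 196 days if best response is settled by the end of Cycle 8. It is up to 532 or 868 days if deepening through Cycle 20 or Cycle 32 resets best response. These are upper limits that assume first response at Cycle 2 Day 1 and no cycle delays; patients whose first response is their best lose nothing. The documents do not say how many patients deepen or when, so the effect on the reported median cannot be fixed from them.

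Separately, DOR and PFS name different end events. The clear gap is death, which is a PFS event, is absent from 6.3.4, and has no censoring rule in 10.3.2. The status of relapse from CR is unresolved for both endpoints.

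The primary toxicity analysis, N = 45, and the ORR and OS definitions are unaffected. PFS is affected only in that the status of relapse from CR needs stating.

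**What to change.** In 6.3.4 and 10.3.2:
- Define DOR among responders, from the first documented (subsequently confirmed) PR or better to the same progression event used for PFS.
- State whether relapse from CR counts as that event, and apply the answer to both DOR and PFS, with a matching line in 6.3.5.
- State how death without progression is handled, and give the censoring rule.
- If time from best response is wanted, keep it as a separately named descriptive endpoint, and say whether responses that deepen after Cycle 8 reset the best-response date.

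The cost is wording. First-response dates should be derivable from the assessments already scheduled in 6.3.1, so no new visit, test or patient is needed. Response results on the first 20 patients have already been presented (1.2.10), so the change should be dated and both durations reported.

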6.3.5 Progression-Free Survival

PFS is defined as time of start of treatment to time of progression or death, whichever occurs first.

6.3.6 Overall Survival

Overall survival is defined as the time of start of treatment to death from any cause.

6.3.7 Overall response rates after 8 cycles

Overall response rates (ORR) is PR+VGPR+CR after 8 cycles of therapy.

6.4 TOXICITY CRITERIA

The following adverse event management guidelines are intended to ensure the safety of each patient while on the study. The descriptions and grading scales found in the revised NCI Common Terminology Criteria for Adverse Events (CTCAE) version 4.0 will be utilized for AE

reporting. All appropriate treatment areas should have access to a copy of the CTCAE version 4.0. A copy of the CTCAE version 4.0 can be downloaded from the CTEP web site (http://ctep.cancer.gov/protocolDevelopment/electronic_applications/ctc.htm#ctc_40).

6.4.1 Attribution of the AE

- Definite: The AE *is clearly related* to the study treatment.
- Probable: The AE *is likely related* to the study treatment.
- Possible: The AE *is may be related* to the study treatment.
- Unlikely: The AE *is doubtfully related* to the study treatment.
- Unrelated: The AE *is clearly NOT related* to the study treatment.

7 NIH REPORTING REQUIREMENTS/DATA AND SAFETY MONITORING PLAN

7.1 DEFINITIONS

Please refer to definitions provided in Policy 801: Reporting Research Events found [here](#).

7.2 OHSRP OFFICE OF COMPLIANCE AND TRAINING/IRB REPORTING

7.2.1 Expedited Reporting

Please refer to the reporting requirements in Policy 801: Reporting Research Events and Policy 802 Non-Compliance Human Subjects Research found [here](#). Note: Only IND Safety Reports that meet the definition of an unanticipated problem will need to be reported per these policies.

7.2.2 IRB Requirements for PI Reporting at Continuing Review

Please refer to the reporting requirements in Policy 801: Reporting Research Events found [here](#).

7.3 NCI CLINICAL DIRECTOR REPORTING

Problems expeditiously reported to the OHSRP in iRIS will also be reported to the NCI Clinical Director. A separate submission is not necessary as reports in iRIS will be available to the Clinical Director.

In addition to those reports, all deaths that occur within 30 days after receiving a research intervention should be reported via email to the Clinical Director unless they are due to progressive disease.

To report these deaths, please send an email describing the circumstances of the death to [name] at [contact] within one business day of learning of the death.

7.4 NIH REQUIRED DATA AND SAFETY MONITORING PLAN

7.4.1 Principal Investigator/Research Team

The clinical research team will meet once a week when patients are being actively treated on the trial to discuss each patient in detail. Decisions about dose level enrollment and dose escalation if applicable will be made based on the toxicity data from prior patients.

All data will be collected in a timely manner and reviewed by the principal investigator or a lead associate investigator in a timely manner. Events meeting requirements for expedited reporting as described in section 7.2 will be submitted within the appropriate timelines. .

The principal investigator will review adverse event and response data on each patient to ensure

safety and data accuracy. The principal investigator will personally conduct or supervise the investigation and provide appropriate delegation of responsibilities to other members of the research staff.

8 SPONSOR PROTOCOL/SAFETY REPORTING

8.1 DEFINITIONS

8.1.1 Adverse Event

Any untoward medical occurrence in a patient or clinical investigation subject administered a pharmaceutical product and which does not necessarily have a causal relationship with this treatment. An adverse event (AE) can therefore be any unfavorable and unintended sign (including an abnormal laboratory finding), symptom, or disease temporally associated with the use of a medicinal (investigational) product, whether or not related to the medicinal (investigational) product (ICH E6 (R2))

8.1.2 Serious Adverse Event (SAE)

An adverse event or suspected adverse reaction is considered serious if in the view of the investigator or the sponsor, it results in any of the following:

- Death,
- A life-threatening adverse event (see section **8.1.3**)
- Inpatient hospitalization or prolongation of existing hospitalization
 - A hospitalization/admission that is pre-planned (i.e., elective or scheduled surgery arranged prior to the start of the study), a planned hospitalization for pre-existing condition, or a procedure required by the protocol, without a serious deterioration in health, is not considered a serious adverse event.
 - A hospitalization/admission that is solely driven by non-medical reasons (e.g., hospitalization for patient convenience) is not considered a serious adverse event.
 - Emergency room visits or stays in observation units that do not result in admission to the hospital would not be considered a serious adverse event. The reason for seeking medical care should be evaluated for meeting one of the other serious criteria.
- Persistent or significant incapacity or substantial disruption of the ability to conduct normal life functions
- A congenital anomaly/birth defect
- Important medical events that may not result in death, be life-threatening, or require hospitalization may be considered a serious adverse drug experience when, based upon appropriate medical judgment, they may jeopardize the patient or subject and may require medical or surgical intervention to prevent one of the outcomes listed in this definition.

8.1.3 Life-threatening

An adverse event or suspected adverse reaction is considered "life-threatening" if, in the view of

either the investigator or sponsor, its occurrence places the patient or subject at immediate risk of death. It does not include an adverse event or suspected adverse reaction that, had it occurred in a more severe form, might have caused death. (21 CFR312.32)

8.1.4 Severity

The severity of each Adverse Event will be assessed utilizing the CTCAE version 4.0.

8.1.5 Relationship to Study Product

All AEs will have their relationship to study product assessed using the terms: related or not related.

- Related – There is a reasonable possibility that the study product caused the adverse event. Reasonable possibility means that there is evidence to suggest a causal relationship between the study product and the adverse event.
- Not Related – There is not a reasonable possibility that the administration of the study product caused the event.

8.2 ASSESSMENT OF SAFETY EVENTS

AE information collected will include event description, date of onset, assessment of severity and relationship to study product and alternate etiology (if not related to study product), date of resolution of the event, seriousness and outcome. The assessment of severity and relationship to the study product will be done only by those with the training and authority to make a diagnosis and listed on the Form FDA 1572 as the site principal investigator or sub-investigator. AEs occurring during the collection and reporting period will be documented appropriately regardless of relationship. AEs will be followed through resolution.

SAEs will be:

- Assessed for severity and relationship to study product and alternate etiology (if not related to study product) by a licensed study physician listed on the Form FDA 1572 as the site principal investigator or sub-investigator.
- Recorded on the appropriate SAE report form, the medical record and captured in the clinical database.
- Followed through resolution by a licensed study physician listed on the Form FDA 1572 as the site principal investigator or sub-investigator.

For timeframe of recording adverse events, please refer to section [6.1](#). All serious adverse events recorded from the time of first investigational product administration must be reported to the sponsor with the exception of any listed in section [8.4](#).

8.3 REPORTING OF SERIOUS ADVERSE EVENTS

Any AE that meets protocol-defined serious criteria or meets the definition of Adverse Event of Special Interest that require expedited reporting must be submitted immediately (within 24 hours of awareness) to OSRO Safety using the CCR SAE report form. Any exceptions to the expedited reporting requirements are found in section [8.4](#).

All SAE reporting must include the elements described in section **8.2**.

SAE reports will be submitted to the Center for Cancer Research (CCR) at: [contact] and to the CCR PI and study coordinator. CCR SAE report form and instructions can be found at: <https://ccrod.cancer.gov/confluence/pages/viewpage.action?pageId=157942842>

Following the assessment of the SAE by OSRO, other supporting documentation of the event may be requested by the OSRO Safety and should be provided as soon as possible.

8.4 WAIVER OF EXPEDITED REPORTING TO CCR

As death due to disease progression is part of the study objectives, and captured as an endpoint in this study, it will not be reported in expedited manner to the sponsor. However, if there is evidence suggesting a causal relationship between the study drug and the event, report the event in an expedited manner according to section **8.3**.

8.5 SAFETY REPORTING CRITERIA TO THE PHARMACEUTICAL COLLABORATORS

All events listed below must be reported in the defined timelines to [contact]. The CCR Office of Regulatory Affairs will send all reports to the manufacturer as described below.

8.5.1 SAE Reporting to Amgen

All SAEs, except for TLS, occurring after the subject has signed the informed consent form (ICF) until 30 days after the last dose of any study treatment must be fully documented and reported to Amgen Global Safety as soon as possible but no later than 7 calendar days of initial receipt of the information. **All cases of TLS must be reported to Amgen as a Serious Adverse Event (SAE) through the normal process within 24 hours of the clinical site becoming aware of the event**

The SAE report forms and the SAE Supplemental Form or MedWatch Form 3500a should be faxed/mailed together to Amgen Global Safety.

[contact] (toll-free, US only)
Toll-free Number: [contact]
Email: [contact]

8.5.2 SAE Reporting to Celgene

All adverse experience reports must include the patient number, age, sex, weight, severity of reaction (e.g. mild, moderate, severe), relationship to drug (e.g. probably related, unknown relationship, definitely not related), date and time of administration of test medications and all concomitant medications, and medical treatment provided. The investigator is responsible for evaluating all adverse events to determine whether criteria for “serious” and as defined above are present. The investigator is responsible for reporting adverse events to Celgene as described below.

Serious adverse events (SAE) are defined above. The investigator must inform Celgene in writing using a Celgene SAE form or MEDWATCH 3500A form of any SAE as soon as possible or at least within 24 hours of being aware of the event. The date of awareness should be noted on the report. The written report must be completed and supplied to Celgene by facsimile within 24 hours/1 business day at the latest on the following working day. The initial report must be as

complete as possible, including an assessment of the causal relationship between the event and the investigational product(s), if available. Information not available at the time of the initial report (e.g., an end date for the adverse event or laboratory values received after the report) must be documented on a follow-up report. A final report to document resolution of the SAE is required. The Celgene tracking number (RV-MM-PI-0663) and the institutional protocol number should be included on SAE reports (or on the fax cover letter) sent to Celgene. A copy of the fax transmission confirmation of the SAE report to Celgene should be attached to the SAE and retained with the patient records.

Celgene Corporation
Drug Safety
[name]
[name]
Toll Free: [contact]
[contact]
[contact]

